9.3 Appendix 3: Simulation Studies

The number of incidence x has the binomial distribution given the probability parameter π :

$$p(x|\pi) = \binom{n}{x} \pi^x (1 - \pi)^{n-x}, \quad x=0, 1, \dots, n \quad (1)$$

We assume the distribution for π follows beta distribution with parameters α and β :

$$p(\pi) = \text{Beta}(\alpha, \beta) = \frac{1}{B(\alpha, \beta)} \pi^{\alpha-1} (1 - \pi)^{\beta-1}, \quad 0 < \pi < 1 \quad (2)$$

where $B(\alpha, \beta)$ is a beta function

$$B(\alpha, \beta) = \frac{\Gamma(\alpha)\Gamma(\beta)}{\Gamma(\alpha+\beta)}.$$

Then the posterior distribution is a beta distribution as well

$$p(\pi|x) = \frac{p(x|\pi)p(\pi)}{p(x)} \sim \pi^x (1 - \pi)^{n-x} \pi^{\alpha-1} (1 - \pi)^{\beta-1} \\ \sim \pi^{(\alpha+x)-1} (1 - \pi)^{(\beta+n-x)-1} = \text{Beta}(\hat{\alpha}, \hat{\beta}), \quad (3)$$

where $\hat{\alpha} = \alpha + x$ and $\hat{\beta} = \beta + n - x$. This conjugate feature of Beta distribution will be used in the simulations below.

We start with a hypothetical scenario where the viremia incidence rate π_i is known ($i = 0$ for placebo and $i = 1$ for vaccine). Let n_1 and n_2 be the cumulative number of subjects each group has at the first and second interim look, respectively. And let N denote the number of subjects each group has at the end of trial.

1. The data at the first interim look will be simulated by drawing $n_1 = 25$ random samples from $\text{binomial}(n_1, \pi_i)$ ($i = 0, 1$). The number of incidence will be denoted as s_{1i} ($i = 0, 1$).
2. Based on the conjugate feature of the beta prior, the distribution of the viremia incidence rate should be updated to $\text{Beta}(\alpha + s_{1i}, \beta + n_1 - s_{1i})$ ($i = 0, 1$) at the first interim look. Draw J random samples for θ_{1i} from the above beta distribution, where θ_{1i} is a random sample of the viremia incidence rate for the i th group ($i = 0, 1$) at the first interim look.
3. For each θ_{1i} draw M random samples from $\text{binomial}(N - n_1, \theta_{1i})$ to simulate the outcomes at the end of trial when all subjects are recruited and followed up for the endpoint ($i = 0, 1$). The number of additional (plus) incidence will be denoted as ps_{1i} ($i = 0, 1$). Consequently, the reduction in relative risk is estimated as $rrr = 1 - \frac{s_{11} + ps_{11}}{s_{10} + ps_{10}}$.
4. Compute the proportion P of $rrr \geq 25\%$ over the $J \times M$ random samples. If $P \leq \text{cutoff}$, here the cutoff a threshold value (say 20%) to be determined the simulation studies, then stop the study. Otherwise proceed to the step below.

5. Draw additional $n_2 - n_1 = 20$ random samples from $binomial(n_2 - n_1, \pi_i)$ ($i = 0, 1$). Suppose the number of incidence is s_{2i} ($i = 0, 1$). The distribution of the viremia incidence rate is now updated to $Beta(\alpha + s_{1i} + s_{2i}, \beta + n_2 - s_{1i} - s_{2i})$ ($i = 0, 1$) at the second interim look. Draw J random samples for θ_{2i} from the above beta distribution, where θ_{2i} is a random sample of the viremia incidence rate for the i th group ($i = 0, 1$) at the second interim look.
6. For each θ_{2i} draw M random samples from $binomial(N - n_2, \theta_{2i})$ to simulate the outcomes at the end of trial when all subjects are recruited and followed up for the endpoint ($i = 0, 1$). The additional number of incidence will be denoted as ps_{2i} ($i = 0, 1$). The reduction in relative risk is estimated as $rrr = 1 - \frac{s_{11} + s_{21} + ps_{21}}{s_{10} + s_{20} + ps_{20}}$.
7. Compute the proportion P of $rrr \geq 25\%$ over the $J \times M$ random samples. If $P \leq cutoff$ then stop the study. Otherwise continue the study to the end when all N subjects are enrolled and followed up for the end point one year after the first injection of study drug.
8. Repeat steps 1-7 R times to estimate the probability of stopping the study at first and second looks for a given hypothetical scenario as the proportion of stopping over the R repetitions.

We repeat the process for various scenarios. Specifically, the scenarios considered are (1) no effect (incidence rates in the two groups are equal), (2) minor effect (10% reduction in incidence rate), (3) meaningful effect (25% reduction in incidence rate), and (4) significant effect (45% reduction in incidence rate). The incidence rates for placebo group considered are 46% and 51%. For each scenario, we run the simulations with $R=1000$, $J=1000$, and $M=1000$.

Simulation results are presented in the tables below.

Table 1: The cumulative probability of the Bayesian predictive probability (BPP) that the viremia incidence rate is at least 25% lower in ASP0113 than that in placebo is less than 25% (futility) at each interim look for different scenarios.

Viremia incidence rate		Cumulative probability of futility			Prob of success
Placebo	ASP0113	1 st look	2 nd look	End of study	End of study
0.51	0.51	0.680	0.921	0.976	0.024
	0.46	0.528	0.827	0.908	0.092
	0.38	0.285	0.520	0.636	0.364
	0.28	0.083	0.155	0.175	0.825
0.46	0.46	0.656	0.882	0.961	0.039
	0.41	0.511	0.766	0.868	0.132
	0.34	0.275	0.510	0.609	0.391
	0.25	0.079	0.172	0.185	0.815

Table 2: The cumulative probability of the Bayesian predictive probability (BPP) that the viremia incidence rate is at least 25% lower in ASP0113 than that in placebo is less than 20% (futility) at each interim look for different scenarios.

Viremia incidence rate		Cumulative probability of futility			Prob of success
Placebo	ASP0113	1 st look	2 nd look	End of study	End of study
0.51	0.51	0.632	0.905	0.971	0.029
	0.46	0.474	0.800	0.897	0.103
	0.38	0.247	0.479	0.614	0.386
	0.28	0.064	0.138	0.159	0.841
0.46	0.46	0.608	0.865	0.957	0.043
	0.41	0.454	0.747	0.862	0.138
	0.34	0.246	0.470	0.594	0.406
	0.25	0.059	0.149	0.164	0.836

Table 3: The cumulative probability of the Bayesian predictive probability (BPP) that the viremia incidence rate is at least 25% lower in ASP0113 than that in placebo is less than 15% (futility) at each interim look for different scenarios.

Viremia incidence rate		Cumulative probability of futility			Prob of success
Placebo	ASP0113	1 st look	2 nd look	End of study	End of study
0.51	0.51	0.579	0.879	0.966	0.034
	0.46	0.425	0.760	0.885	0.115
	0.38	0.195	0.435	0.590	0.410
	0.28	0.046	0.116	0.141	0.859
0.46	0.46	0.554	0.846	0.954	0.046
	0.41	0.385	0.710	0.850	0.150
	0.34	0.205	0.421	0.567	0.453
	0.25	0.045	0.118	0.137	0.863

When there is no treatment effect (0.46 vs 0.46 or 0.51 vs. 0.51) the $BPP \leq 0.25$ criterion results in >65% chance to terminate the study; $BPP \leq 0.2$ criterion results in about 61% chance while $BPP \leq 0.1$ offers less than 50% chance which is too low to serve our purpose since the goal of the interim analysis is to stop early when there is no treatment effect.

When there is a fair treatment effect (25% reduction in viremia rate) (0.46 vs 0.34 or 0.51 vs. 0.38) the $BPP \leq 0.25$ criterion results in 30% chance to terminate the study while $BPP \leq 0.2$ criterion results in about 23% chance.

The chance of mistakenly terminating study at interim for the 0.46/0.25 and 0.51/0.28 scenarios is about 7% to 9% for the 0.2 criterion and >10% for the 0.25 criterion.

Overall, the 0.2 cutoff performs well in terms of stop early when there is no treatment effect and the chance not to kill the study when there is a fair treatment effect.

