7.8 Interim Analysis (and Early Discontinuation of the Clinical Study)

No interim analysis evaluating the efficacy results are planned. The safety data will be monitored by the DMC according to the DMC Charter. Futility analyses with first 50 subjects and with 90 subjects were conducted ([Appendix 2](#)). The details will be described in the clinical study report.

At each futility analysis, Bayesian predictive probability of success (*BPP*) that the overall results of the trial will achieve the desired outcome, i.e., viremia rate on ASP0113 is at least 25% less than that on placebo, will be calculated based on the accrued data. If $BPP \leq 0.20$, then we conclude ASP0113 meets futility criterion.

The 20% cut-off for BPP is determined by simulation studies. The simulation studies cover the following scenarios: for each placebo viremia rate of 0.40, 0.46, and 0.51 the reduction in viremia due to ASP0113 run from 0% (no effect), 10% (marginal reduction), 25% (meaningful reduction), and 45% (significant reduction). Under each scenario, BPP is calculated at each interim look. The 20% cutoff produces satisfactory overall operating

characteristics of stopping the study early when there is little effect and preserving the power when ASP0113 shows the hypothesized effect.

A Data Monitoring Committee (DMC), external from the Sponsor, will be established to review safety and efficacy data at each interim look. A detailed description of the DMC, its role in this clinical trial, and the timing of the scheduled reviews will be provided in the DMC Charter.

Production of tables and listings will be performed by the independent statistician at Astellas / independent Data Analysis programmer at [REDACTED]. No member of the clinical trial team will have access to the reporting data base or will review the final tables and listings created for the DMC.

The primary responsibility of the DMC will be to monitor the trial for safety and futility concerns. The DMC will not stop the trial based on efficacy advantages. Therefore, the significance level need not be adjusted for the interim looks.

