9.2 Appendix 2: Futility Analysis

The decision rule for stopping the trial based on efficacy is outlined below:

1. At the interim look, suppose we have cumulative n_i ($i = 0, 1$) subjects from treatment i ($i = 0$ for placebo and $i = 1$ for vaccine). The cumulative number of subjects with viremia in treatment i will be denoted as s_i ($i = 0, 1$).
2. The additional number of subjects with viremia at the end of trial could be any integer between 0 and $N - n_i$ for treatment i , where N is the total number of subjects planned for each group. The probability that there are additional k_0 subjects with viremia in the placebo group and k_1 subjects with viremia in the vaccine group at the end of trial is

$$p(k_0, k_1) = \binom{N - n_0}{k_0} \frac{B(\alpha + s_0 + k_0, \beta + N - s_0 - k_0)}{B(\alpha + s_0, \beta + n_0 - s_0)} \\ \times \binom{N - n_1}{k_1} \frac{B(\alpha + s_1 + k_1, \beta + N - s_1 - k_1)}{B(\alpha + s_1, \beta + n_1 - s_1)} \quad (\text{A})$$

where α and β are some arbitrary prior parameters and $B(a, b) = \int_0^1 x^{a-1}(1-x)^{b-1}dx$ is a beta function. (For this study, we use $\alpha = 0.6$, $\beta = 0.4$.) The reduction in relative risk is estimated as $rrr = 1 - \frac{s_1 + k_1}{s_0 + k_0}$ with probability (A) above.

3. Sum up the probabilities with which $rrr \geq 25\%$ over all possible values of k_0 and k_1 to get the predictive probability PP :

$$BPP = \sum_{k_0=0}^{N-n_0} \sum_{k_1=0}^{N-n_1} p(k_0, k_1) \text{step}(rrr \geq 25\%)$$

where the *step function* = 1 if $rrr \geq 25\%$ and 0 otherwise.

If $BPP \leq \text{cutoff}$ then ending the study is indicated. Otherwise the study should be continued. Here the *cutoff* = 20% is an empirical value determined by simulation studies.

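### SAP Appendix 3: the second-look stopping rates do not follow from the stated futility rule, and the text choosing the 0.20 cutoff conflicts with its own tables

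*SAP*

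**What the plan says.** Protocol 7.8.2 calls the operating characteristics of the futility rule satisfactory and leaves the details to the SAP. SAP Appendix 2 gives the rule: stop if the Bayesian predictive probability (BPP) of an observed relative reduction of at least 25% at the end of the trial is at or below the cutoff. It says that the cutoff of "20% is an empirical value determined by simulation studies".

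Appendix 3 then gives three tables of cumulative stopping probability, for cutoffs 0.25, 0.20 and 0.15, and argues from them:

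- No effect: the 0.20 "criterion results in about 61% chance while" a cutoff of 0.10 "offers less than 50% chance which is too low to serve our purpose".
- A 25% reduction: the 0.25 cutoff stops 30% of the time, and the 0.20 "criterion results in about 23% chance".
- A 45% reduction: "The chance of mistakenly terminating study at interim for the 0.46/0.25 and 0.51/0.28 scenarios is about 7% to 9% for the 0.2 criterion", against more than 10% for 0.25.

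It concludes: "Overall, the 0.2 cutoff performs well in terms of stop early when there is no treatment effect".

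SAP 7.8 says that the simulations were run "for each placebo viremia rate of 0.40, 0.46, and 0.51". It also reports: "Futility analyses with first 50 subjects and with 90 subjects were conducted".

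**The concern.** The wrongful-stop sentence agrees with neither column of Table 2. The no-effect figure is the first-look value, although the rule is applied at two looks and the tables are cumulative. That raised two questions: whether the tables follow from the stated rule, and whether the three cutoffs were compared on one basis.

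These are the only operating characteristics given for the stopping threshold. A reader who wants the chance of stopping a vaccine with a true 25% reduction, which the SAP itself calls meaningful, finds 23% in the text and 47-48% in the table.

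**Working it through.** **Inputs**

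- Looks at 25 and 45 subjects per arm, with data accumulating (SAP 3.2; Appendix 3, steps 1 and 5).
- Prior Beta(0.6, 0.4) in each arm; success is an observed relative reduction of at least 25% (Appendix 2).
- Final size N per arm: Appendix 3 gives no number. SAP 4 gives 64 (for power) and 70 (to be enrolled). Both were used, which produces the ranges below.
- R = 1000 simulated trials (Appendix 3).

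**Method.** For every pair (s0, s1) at n = 25 and n = 45, BPP is the sum of formula (A) over all (k0, k1) with s1 + k1 ≤ 0.75 × (s0 + k0). The chance of stopping at look 1 is the sum of Bin(s0; 25, π0) × Bin(s1; 25, π1) over pairs with BPP ≤ cutoff. Paths that do not stop gain 20 subjects per arm, and those with BPP ≤ cutoff at n = 45 are added. This is exact, with no sampling noise.

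**First look.** With z = (table − exact) / √(exact × (1 − exact) / 1000), all 24 cells lie between −1.5 and +1.7. The formula, prior and first-look size are therefore read correctly.

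**Second look, cutoff 0.20**

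| Placebo / ASP0113 | Exact, cumulative | Table 2 |
|---|---|---|
| 0.46 / 0.46 | 80.5-81.8% | 86.5% |
| 0.51 / 0.51 | 83.8-85.1% | 90.5% |
| 0.46 / 0.34 | 35.3-36.7% | 47.0% |
| 0.51 / 0.38 | 36.3-37.9% | 47.9% |
| 0.46 / 0.25 | 9.2-9.7% | 14.9% |
| 0.51 / 0.28 | 8.3-8.8% | 13.8% |

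Example, 0.46 / 0.34 with N = 70: SE = √(0.353 × 0.647 / 1000) = 0.015; gap = 0.470 − 0.353 = 0.117; z = 7.7. Over all 24 cells of the three tables the excess is 4.2 to 12.9 points, or 3.6 to 8.5 SE, always in the same direction. At N = 64 the largest gap is still 10.6 points.

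A 200,000-trial simulation of Appendix 3, steps 1-7, agrees with the exact values at N = 70: 0.804 for 0.46/0.46, 0.355 for 0.46/0.34, 0.093 for 0.46/0.25 and 0.083 for 0.51/0.28. Varying N from 46 to 140, the second-look size from 45 to 70, the prior, or using a fresh second sample did not reproduce the published column.

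**Text against tables**

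| Scenario, cutoff | Text | Table, look 1 | Table, by look 2 | Exact, by look 2 |
|---|---|---|---|---|
| No effect, 0.20 | about 61% | 60.8-63.2% | 86.5-90.5% | 80.5-85.1% |
| 25% reduction, 0.20 | about 23% | 24.6-24.7% | 47.0-47.9% | 35.3-37.9% |
| 25% reduction, 0.25 | 30% | 27.5-28.5% | 51.0-52.0% | 40-42% |
| 45% reduction, 0.20 | 7-9% | 5.9-6.4% | 13.8-14.9% | 8.3-9.7% |
| 45% reduction, 0.25 | >10% | 7.9-8.3% | 15.5-17.2% | 10.6-11.6% |
| No effect, 0.10 | <50% | no table | no table | 72.3-77.9% |

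At cutoff 0.10 the exact first-look values under no effect are 47.3% (0.46) and 51.0% (0.51). By look 2, that cutoff stops a 25% reduction 25-28% of the time and a 45% reduction 4.6-5.4%.

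**Remaining slips.** Appendix 3 lists only placebo rates 46% and 51% and shows no rows for 0.40. The exact cumulative values at cutoff 0.20 would be 76-78% (0.40/0.40), 37-39% (0.40/0.30) and 11.4-11.9% (0.40/0.22). In Table 3, row 0.46/0.34, futility and success add to 0.567 + 0.453 = 1.020.

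**The case against.** The strongest counter-reading is that the 7-9% sentence reports the second-look increment of Table 2: 0.138 − 0.064 = 7.4% and 0.149 − 0.059 = 9.0%. The match is close, but the same sentence gives more than 10% for cutoff 0.25, where the increments are 0.155 − 0.083 = 7.2% and 0.172 − 0.079 = 9.3%. The exact cumulative values fit both halves of the sentence; the increments fit only one. Where the text's figures came from remains inference.

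The sources of the 23% and 30% figures are also uncertain. The Table 2 increments for a 25% reduction (0.470 − 0.246 = 22.4%; 0.479 − 0.247 = 23.2%) are nearer to 23% than its first-look values are. Either way, neither figure is the chance of stopping over two looks. Likewise, the figure for 0.10 is only presumably a first-look value; what is certain is that no table supports it.

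Appendix 2 defines N as the planned number per group, so 70 is the natural reading. That is accepted, and 64 serves as a sensitivity case with the same conclusion. SAP 7.8 also describes the desired outcome as a 25% reduction, but Appendix 3 does not say that this defines its end-of-study success column. For 0.46/0.25 at cutoff 0.20, end-of-study futility is 13.2-13.7% under that definition and 19.7-21.5% under a one-sided 5% chi-square test (table: 16.4%). That column is therefore not counted as an error.

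It is also true that the row adding to 1.02 is one of 24 and minor, and that both futility analyses have already been conducted.

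**Conclusion.** The concern holds. The second-look columns of Tables 1-3 do not follow from the rule in Appendix 2 with the stated looks and prior, and simulation error cannot explain gaps of 4.2 to 12.9 points in all 24 cells. The 7-9% sentence is roughly right and Table 2 is wrong, so 14-15% is not the true wrongful-stop risk. For no effect and for a 25% reduction, the text understates the chance of stopping over two looks. A true 25% reduction is stopped about 35-38% of the time at cutoff 0.20.

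The figures assume Beta(0.6, 0.4), equal arms of 25 and 45 at the looks, and N of 64 to 70 per arm. The figure of more than 10% for cutoff 0.25 stands. Why the tables are wrong is not known. The looks are futility-only and already done, so no stopping decision and no type 1 error changes. The result does not show that 0.20 was a bad choice; it shows that the stated justification cannot be relied on. It should be fixed.

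**What to change.** - Recompute Tables 1-3 by exact enumeration of formula (A), stating N and the end-of-study success criterion.
- Add rows for placebo 0.40, and either add a table for cutoff 0.10 or delete that comparison.
- Restate the 61%, 30%, 23%, below-50% and 7-9% sentences as cumulative over both looks; leave the one for more than 10%.
- Correct the Table 3 row (if 0.567 is right, success is 1 − 0.567 = 0.433).
- Base the conclusion on the corrected figures, stating that a true 25% reduction is stopped about 35-38% of the time.
- Optionally report the power cost of the looks at 0.46/0.25. For an unstratified one-sided chi-square test, power falls from 83.5% to 80.3% at 70 per arm and from 81.1% to 78.5% at 64. The planned CMH test is stratified, so these are approximations.

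The cost is seconds of computing and a corrected appendix or a note in the clinical study report, where SAP 7.8 already promises the futility details. For 0.46 placebo, stated wrongful stopping falls from 14.9% to about 9% and stopping at a 25% reduction from 47% to about 36%. Stopping under no effect falls from 86.5% to about 81%.

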9.4 Appendix 4: List of the SAP Changes and Rationale

The changes to the approved SAP (15April 2014) that affect the analyses are specified with the rationale in the table below.

SAP Sections	Description	Rationale
5.2 Per Protocol Set (PPS)	Removed.	For a Phase 2 study, this type of analysis where a sizable number of patients are excluded from the PPS classification criteria may provide uninterpretable results.
6.1.2 Secondary Efficacy Endpoints	Removed one of the secondary efficacy endpoint of subject survival through one year.	In order to avoid redundancy as as the mortality is summarized as a part of adverse event summary.
7.1 General Consideration	Specified the analysis duration of the primary study period as data collected through day 380 (=365+14+1) for this SAP.	This analysis duration is specified by taking the protocol allowed visit windows in order to clarify the data inclusion for this analysis plan.
7.2.2 Protocol Deviation	Removed the category of PD5-Other.	In order to capture the protocol deviations to specific categories utilizing PD1 through PD4.
7.4.1.2 Sensitivity Analysis for Primary Efficacy Endpoint	
 Clarified the analysis to assume a patient with at least 2 consecutive missing central laboratory viral load as a CMV viremic, and Added an analysis to consider a patient who took AVT that is adjudicated as a CMV viremia treatment but no evidence of CMV viremia by central laboratory is assumed CMV viremic. 	These sensitivity analyses are planned in order to evaluate the robustness of the primary analysis for the primary efficacy endpoint.
7.4.3 Analysis of Exploratory Endpoints	The assessments of kidney transplantation and SF-12 questionnaires to be only listed without a formal analysis within this analysis plan.	A proper analysis for these questionnaires to be conducted by the HEOR expert.
7.5.2 Adverse Events of Special Interest	Removed the following AEs of special interest: 
 Opportunistic infections Special infections related to kidney transplant Post-transplant lymphoproliferative disorder 	The opportunistic infection is a prespecified exploratory efficacy endpoint thus removed from this section in order to avoid redundancy. The second and third bullet items are removed because these events are not expected to occur under vaccine treatment.
7.5.3 Clinical Laboratory Evaluation	Removed the shift summary for laboratory parameters using low, normal and high normal ranges.	The laboratory values are summarized for the change from baseline using the descriptive statistics.

7.5.3 Clinical Laboratory Evaluation	Removed the following: 
 • Potentially clinically significant (PCS) laboratories • Shift tables for SGOT, SGPT, Platelets, Hematocrit, Hemoglobin, Serum creatinine, and Total bilirubin at granular categories 	This type of analysis is considered medically not meaningful.
7.5.3.1 Liver Function Test	The criteria are updated to the following: 
 • ALT or AST > 3xULN, > 5xULN, > 10xULN, >20xULN • ALT > 3xULN, > 5xULN, > 10xULN, >20xULN • AST > 3xULN, > 5xULN, > 10xULN, >20xULN • ALP > 1.5xULN, >3xULN • Total Bilirubin >2xULN • ALT or AST > 3xULN and Total Bilirubin > 1.5xULN • ALT or AST > 3xULN and Total Bilirubin > 2xULN • ALT or AST > 3xULN and ALP < 2xULN and Total Bilirubin > 2xULN 	These new criteria are the sponsor's standard categories.
7.5.4 Vital Signs	Removed the summary of potentially significant vital signs based on special criteria.	The vital sign is summarized for the mean change from baseline using the descriptive statistics.
7.8 Subgroups of Interest	Removed the subgroup analysis on adverse events of special interest for the various subgroup factors.	This type of subgroup analysis on potentially small number of patients with AEs of special interest may yield uninterpretable results.

